The treatment for this trial will be an initial aliquot of donor stool in 90ml of sterile saline, followed by weekly ingestion of six capsules of encapsulated fecal material. These will be provided by the Microbiome Health Research Institute at Massachusetts Institute of Technology as described in their Drug Master File (15543).

Dosage Form

1. Initial dose - filtered solution of donor stool (50 g) homogenized with sterile saline 90 mL.
2. Maintenance dose – six capsules of fecal material taken once per week (550µl of fecal material in size 00 gelatin capsule)

Dosing Regimen

Single initial dose of 90mL of fecal solution

Weekly dose of 6 capsules of fecal material (total 3300µl of fecal material per week)

Packaging

Fecal solution will be acquired in plastic bottles, and encapsulated fecal material in blister packs from the Microbiome Health Research Institute at Massachusetts Institute of Technology, as described in their Drug Master File (15543).

Labeling

See Drug Master File (15543).

Sequence & Duration of Trial Periods

An outline of the study timeline and measurements is shown in Appendix 1

Recipient Procedures:

Week -1; Screening – potential subjects will undergo the following screening procedures one week prior to FMT to determine if they meet the recipient selection criteria;

- medical record review to confirm diagnosis and treatment history
- Harvey Bradshaw Index (HBI) score to determine disease activity score (Appendix 2)
- stool sample to exclude current infections (bacterial culture, ova & parasites, Clostridium difficile toxin)
- standard of care blood tests for baseline and infection screening (CBC, LFTs, Renal profile, CRP, ESR)
- stool sample for microbiome analysis (MIT)

Women of child-bearing potential will be counseled by study clinicians, that those who choose to the treatment arm will be requested to avoid pregnancy by hormonal or barrier methods from time of screening for 7 months (duration of FMT therapy and one month lag afterwards).

Eligible subjects will then have the option to be in either treatment or control arm.

Week 0: Treatment & Control Arm

- Urine pregnancy test (HCG) for females of child-bearing age (during admission process, prior to colonoscopy)
- Initial Fecal Transplant via colonoscopy for treatment arm (none for control arm). Biopsies will be taken at the time of colonoscopy

Week 1: Treatment Arm

- Ingestion of first oral FMT capsules in clinic, under observation

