- Follow-up phone call to assess for adverse events 4 hours later

Week 2, 4, 8, 10, 12, 16, 20 and 26: (Treatment & Control Arms)

- Stool sample for microbiome analysis (MIT)

Weeks 4, 12, 26: (Treatment & Control Arms) ;

Follow-up assessment of

- clinical scores
- adverse event screening,
- standard of care blood tests screening (CBC, LFTs, Renal profile, CRP, ESR)

Week 26: (Treatment & Control Arms);

Efficacy end-point evaluation;

- Urine pregnancy test (HCG) for females of child-bearing age (prior to colonoscopy)
- colonoscopy and Rutgeert's score of anastomosis images (Appendix 3). Biopsies will be taken at the time of the colonoscopy

Week 52 (Treatment & Control Arms)

- Final safety assessment; phone interview to screen for adverse events.

Written instructions will be given to all subjects for stool collection methods (Appendix 4).

Stopping Criteria

Adverse events will be specifically monitored at 4, 12, 26 and 52 weeks after FMT by direct patient interviews, or by reporting from clinical sites of adverse events at any time in-between. A data safety and monitoring board (DSMB, Appendix 5) will review all patient data to ensure optimal patient safety and precautions for subjects with CD treated with FMT. A severity grade for adverse events (Appendix 6) and subject symptom diary used (Appendix 7). The DSMB will meet a minimum of 2 times: after treatment of the first 20 subjects, and after treatment of all 44 subjects. Study will be stopped under the following circumstances;

- recurrence of CD symptoms in any more than 3 of the first 10 patients treated (increase by >5 points from baseline of mean HBI score after FMT)
- detection of new pathogenic intestinal infection in stool samples in any patient treated.
- any unexpected serious adverse event that that DSMB determines is of significant clinical impact, and probably related to FMT

In addition, any subject who develops a serious adverse event that is judge to be probably, possibly or definitely related to FMT therapy will receive no further FMT treatment. They will remain in the trial for adverse event follow-up.

Accountability Procedures for the Investigational Product

The location, volume and number of all FMT donor solutions will be maintained in a log by the research team. The principal investigator will be responsible for accurate record and tracking of all FMT solutions. Logging of FMT solution used for administration will be performed using a two-person process.

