- Active infections, including, but not limited to, surgical infections or abscesses
- History of severe food allergies
- Any condition, based on clinical judgement, that may make study participation unsafe. In particular, post-operative anastomotic leaks or fistula

Subject Withdrawal Criteria

Patients – patients will be withdrawn under the following circumstances;

- Colonoscopy for FMT cannot be completed for technical reasons due to inability by endoscopist to reach terminal ileum, or patient intolerance of procedure, or pregnancy. These patients will only be followed-up for week 2 adverse event screening, as they will not have received FMT. These subjects will be replaced, as they will not be considered “treated”.
- Patient withdraws their consent for study protocols, follow-up visits or contacts
- Any subject who develops a serious adverse event that is judged to be probably, possibly or definitely related to FMT therapy will receive no further FMT treatment. They will remain in the trial only for adverse event follow-up.

Subjects who require rescue treatment will be censured for the analysis of primary end-point. They will however continue to be followed for 6 months for evaluation of safety outcomes.

6. Treatment of Subjects

Trial Treatment

The initial treatment for this trial will be administration of an initial single infusion of fecal solution to the terminal ileum. Treatment will begin at least 30 days after ileo-cecal resection, but within 50 days of surgery, in the treatment group.

Subsequent FMT administration will be in the form of capsules of frozen FMT material ingested orally once a week. Each subject will ingest six FMT capsules once every seven days for the 6 months of treatment in the trial. The first ingestion will be undertaken in the clinic, where subjects will be monitored for adverse events for 1 hour. A follow-up phone call will be undertaken 4 hours later to screen for adverse events. At this visit, and at weeks 4, 12 subjects will be provided with blister packs of FMT capsules for their subsequent doses. They will be instructed to store the blister packs in a sealed bag (provided) in a domestic freezer at -20°C until each weekly ingestion. A full instruction document for patient is included as Appendix 8.

Medications Permitted

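### Two withdrawal rules in practice remove subjects from the FMT arm only, and Section 9 has no analysis set or missing-score rule to offset this

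*Combined protocol and SAP*

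**What the plan says.** Section 5 (Subject Withdrawal Criteria) contains two rules that matter here.

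- **Failed delivery.** The trigger is: "Colonoscopy for FMT cannot be completed for technical reasons due to inability by endoscopist to reach terminal ileum, or patient intolerance of procedure, or pregnancy". On follow-up: "These patients will only be followed-up for week 2 adverse event screening, as they will not have received FMT". On numbers: "These subjects will be replaced, as they will not be considered" treated. The Section 4 schedule for week 0 reads "Initial Fecal Transplant via colonoscopy for treatment arm (none for control arm").
- **FMT-related SAE.** Anyone with a "serious adverse event that is judged to be probably, possibly or definitely related to FMT therapy will receive no further FMT treatment". Section 5 continues: "They will remain in the trial only for adverse event follow-up". Section 4 (Stopping Criteria) gives the same rule as "They will remain in the trial for adverse event follow-up", without the limiting word.

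Section 5 also has a third rule, with no arm restriction: subjects who need rescue treatment are censored for the primary endpoint and followed for safety. Section 6 lists hospitalization among the rescue options for clinical recurrence.

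Section 9 compares the proportion with recurrence in each arm by chi-square or Fisher's exact test. It does not say which subjects form the denominator or how a subject without a week 26 Rutgeerts score is counted.

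**The concern.** Both triggers arise after the subject has chosen an arm, and both depend on FMT. A failed FMT colonoscopy leads to replacement. Under the Section 5 wording, an FMT-related SAE leaves the subject without a planned week 26 endoscopic score. Controls pass through neither filter.

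The filters may be related to outcome. A terminal ileum that cannot be reached may reflect worse post-surgical anatomy. Section 8 counts hospitalization as serious, and a possible relation to FMT is enough to trigger the SAE rule, so a flare admission could qualify. If such subjects are more likely to recur, removing them lowers the observed FMT rate for reasons unrelated to treatment. At about 22 subjects per arm, a few removals are visible in the result. The arms are already self-selected, and this would be a second, avoidable selection step on one side.

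**Working it through.** **Inputs from the documents.** Section 9: 60% recurrence in controls, 20% with FMT, 22 per arm, 80% power, p < 0.05, chi-square or Fisher's exact if any cell is below 5. A two-sided test is assumed, since Section 9 does not state sidedness for the primary test.

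**Inputs assumed.** The documents give no frequency for either rule and no outcome for removed subjects. The number removed, k, is taken as 1 to 3, and their recurrence risk, r, as 0 to 100%.

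**1. The plan's own figure.** The pooled normal formula gives (1.96 × √(2 × 0.4 × 0.6) + 0.842 × √(0.6 × 0.4 + 0.2 × 0.8))² / 0.4² = 22.3 per arm. The arcsine formula gives 21.99. Power at 22 per arm is 79.4% by normal approximation. The stated 22 is reproduced.

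**2. FMT rate if removed subjects are restored.** With 22 evaluable FMT subjects at 20%:

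rate = (22 × 0.20 + k × r) / (22 + k)

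| k | r = 0 | r = 20% | r = 60% | r = 100% |
|---|---|---|---|---|
| 1 | 4.4/23 = 19.1% | 4.6/23 = 20.0% | 5.0/23 = 21.7% | 5.4/23 = 23.5% |
| 2 | 4.4/24 = 18.3% | 4.8/24 = 20.0% | 5.6/24 = 23.3% | 6.4/24 = 26.7% |
| 3 | 4.4/25 = 17.6% | 5.0/25 = 20.0% | 6.2/25 = 24.8% | 7.4/25 = 29.6% |

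The shift is k(r − 0.20)/(22 + k). It is zero when removed subjects recur at the arm's own rate, at most +9.6 points (k = 3, r = 100%) and at least −2.4 points (k = 3, r = 0), against an assumed effect of 40 points.

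**3. Chance of a false finding.** Take 60% recurrence in both arms, 22 per arm, the planned test, and removal from the FMT arm without replacement. By exact enumeration, the chance of a significant result favouring FMT is 2.0% with no removals. For k = 1, 2, 3 it is 4.2%, 4.5%, 7.8% if every removed subject would have recurred, and 2.0%, 1.0%, 0.8% if none would have. These are the two extremes.

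**4. One table near the planning assumptions.** With 13/22 controls and 4/22 FMT subjects recurring, Fisher's test gives p = 0.012. Restoring excluded recurrences to the FMT arm (now chi-square, since no cell is below 5) gives 7/25, p = 0.031; 8/26, p = 0.049; 9/27, p = 0.071. Significance is lost only at five restored recurrences, more than the 1 to 3 assumed above.

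**The case against.** A reader might infer that the rules bias the comparison in one direction, towards FMT. The documents do not support that. Nothing in them says how removed subjects would fare. Intolerance of the procedure and pregnancy have no stated link to recurrence, and pregnancy is an exclusion for all subjects. The failed-delivery rule acts before any FMT is given, in patients whose margins and anastomosis had to be free of active inflammation and who had to be able and willing to undergo colonoscopy. If removed subjects recur less often than the arm, the exclusion works against FMT.

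A reader might also infer that a hospitalized control always stays in the comparison. That conflicts with Sections 5 and 6: hospitalization for clinical recurrence is a rescue option, and rescued subjects in either arm are censored. If controls recur more often, this rule could remove more likely recurrers from the control arm and offset the other two. Nor does a control whose anastomosis cannot be reached at week 26 clearly stay in, because the plan does not say how an absent score is counted.

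Finally, removal under the SAE rule is implied by one of two inconsistent wordings and is not stated as an analysis rule. Such events may also be rare: Sections 2 and 8 report no serious events with FMT in earlier experience.

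All of this stands and limits the claim. What remains is that a control is not withdrawn and replaced for failed FMT delivery, and a control's SAE that is not a rescue event does not end efficacy follow-up. Section 9 offers nothing to offset either difference.

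**Conclusion.** The point holds as an arm-specific exclusion that can bias the primary comparison. Bias in favour of FMT is the most plausible direction, because an unreachable ileum or a possibly related flare admission may go with recurrence. That is a judgement, not something the documents establish. The asymmetry is confined to failed delivery and to FMT-related SAEs that are not already rescue events.

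The size depends on two unknowns, the number removed and their recurrence risk. For 1 to 3 subjects the movement runs from 2.4 points down to 9.6 points up, including none at all. By itself this is unlikely to overturn an effect as large as the plan assumes, but it could matter for a smaller or borderline one.

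**What to change.** - Reconcile the SAE rule in Section 4 (Stopping Criteria) with Section 5, so that stopping FMT does not end efficacy follow-up. No treatment rule needs to change.
- Keep consenting subjects with failed delivery or an FMT-related SAE in the week 26 assessment already scheduled, where a colonoscopy is feasible.
- In Section 9, define the primary analysis set by the arm chosen at enrolment. Any replacement subject is then additional to the withdrawn subject, not a substitute in the denominator.
- State one rule for both arms for subjects without a week 26 score. One option is to count them as recurrences, with a complete-case sensitivity analysis. The rule also covers subjects who cannot have the colonoscopy. Say how it fits with the censoring of rescued subjects.
- Report the treated-only set as a secondary analysis.

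The cost is protocol and SAP wording plus a week 26 visit for a few subjects. The downside is that a few undelivered treatments slightly dilute the estimated effect. Because patients choose their arm, an analysis by chosen arm does not have the protection that randomization would give, and confounding by self-selection has to be addressed separately.

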A recent randomized controlled trial of 17 patients treated with FMT (given by duodenal lavage) for *Clostridium difficile* infection reported their short-term adverse events. Immediately after the duodenal lavage, patients had diarrhea (in 94%), cramping (in 31%) or belching (in 19%) which all resolved within 3 hours in all cases (15). During follow-up, three patients who were treated with donor feces (19%) had constipation. These adverse events have not been noted when FMT is administered by colonoscopy. In our pilot study in patients with active Crohn's disease, no serious adverse events have been noted, over 6 months of follow-up (13). No other adverse events related to study treatment were reported. On the basis of these data, the following risks can be assumed for FMT;

Known Risks of FMT

- Altered bowel pattern (diarrhea, constipation)
- Cramping
- Belching
- Colonoscopy risks – intestinal perforation (1:5000), bleeding, altered bowel habit

Potential Risks of FMT

- Transmission of pathogenic bacteria, viruses, fungi
- Transmission of allergens
- Alteration in intestinal metabolism

Potential Benefits

- Restoration of fecal diversity
- Prevention of intestinal inflammation
- Prevention of clinical symptoms

Description of and justification for the route of administration, dosage, dosage regimen, and treatment period

Route of Administration

Donor fecal microbiota material will be administered in two formats; via colonoscopy as a solution, and encapsulated with glycerol and cocoa butter in HMCP capsules. For the initial dose, FMT in solution will be sprayed in the terminal ileum via a colonoscope. This route of administration for the initial dose has been selected for a number of reasons;

- Recurrence of inflammation in CD always develops in the region of the anastomosis between the ileum and colon (~2 inches long). This is the area where dysbiosis has been noted as a precursor to macroscopic inflammation. Colonoscopic delivery ensures delivery of FMT to the sites of disease recurrence. The rate of engraftment of donor microbiota when delivered via the oral route is unknown.
- The colonoscopic route of administration has been associated with ~80% efficacy in treating patient with *Clostridium difficile* colitis.

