During the follow-up period after enrollment (6 months), subjects should not take any medications that may prevent recurrence of CD; antibiotics, thiopurines, anti-TNFs, mesalamine. Rescue pathway for CD subjects with clinical recurrence during the study period to be determined by the clinician investigator and based on standard of clinical practice. This may include, but is not limited to the following;

- i. Oral steroids (if not already receiving them or failing them)
- ii. Rectal therapy (5-ASA or steroids)
- iii. IV steroids
- iv. Hospitalization
- v. Anti-TNF therapy
- vi. Surgery

7. Assessment of Efficacy

Primary Clinical Endpoint;

Proportion of patients in each arm of the trial who develop endoscopic recurrence within 6 months of ileo-cecal resection. “Endoscopic recurrence” will be defined as a Rutgeert’s score of \geq to i2.

Secondary Endpoints:

Microbial Endpoints;

- Recipients' fecal microbial diversity and metabolic profiles at 2, 4, 8, 10, 12, 16, 20 and 26 weeks after FMT, when compared to baseline

Inflammatory Endpoints;

- Percentage of patients with normal anastomosis (Rutgeerts score 0) at week 26
- Mean CRP at week 26

Clinical Endpoints;

- Mean Harvey Bradshaw Index (HBI) score at week 26
- Percentage of patients in clinical remission (those with an HBI score at week 26 <5)

Safety Endpoints;

- Number and nature of adverse events at week 4, 12, 26 and 52
- % of patients with adverse events reported at week 4, 12, 26 and 52

8. Assessment of Safety

Patient safety monitoring schedule - although there have been no reported serious adverse events associated with fecal microbiota transplantation (FMT) in patients with recurrent refractory Clostridium difficile or Crohn's disease (CD), we will have a special data safety and monitoring board (DSMB) to ensure optimal patient safety and precautions for subjects with CD treated with FMT. Adverse events will be specifically monitored at 4, 12, 26 and 52 weeks after FMT by direct patient interviews, or by reporting from clinical sites of adverse events at any time in-between. The DSMB will meet a minimum of 2 times: after treatment of the first 20 subjects, and after treatment of all 44 subjects. A copy of the DSMB charter is located in Appendix 5.

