For this trial, an adverse event (AE) is defined as any untoward medical occurrence in a patient or clinical investigation patient administered a biologic product; such an occurrence does not necessarily have to have a causal relationship with this treatment. An AE can be any unfavorable and unintended sign, symptom, or disease temporally associated with the use of a medicinal product whether or not considered related to the medicinal product. A serious adverse event (SAE) is defined as any untoward medical occurrence that results in death, is life threatening, requires hospitalization or prolongation of existing hospitalization, results in persistent or significant disability/incapacity, is a congenital anomaly/birth defect, is an important medical event that may not be immediately life threatening or result in death or hospitalization but may jeopardize the patient or may require intervention to prevent one of the other outcomes previously mentioned. Adverse events will be determined by a toxicity grading scale (Appendix 6). In accordance with applicable policies of the BIDMC Institutional Review Board (IRB), the investigator-sponsor will report, to the IRB, any observed or volunteered Unanticipated Problem that is determined to be 1) unexpected; 2) related or at least possibly related to study participation; and 3) suggests that the research places subjects or others at a risk of unknown harm or addition/increased frequency of harms (including physical, psychological, economic, legal, or social harm) than was previously known or recognized. Unanticipated problems may be adverse events, protocol deviations, noncompliance or other types of problems, but MUST meet all of the criteria listed above. Unanticipated problem reports will be submitted to the IRB in accordance with the respective IRB procedures.

Patients will be asked to document their symptoms using the symptom diary card (Appendix 7) as a memory aide. Subjects will be asked to complete a symptom diary card 1 week prior to colonoscopy FMT and on the day of colonoscopy FMT treatment to assess their baseline. They will then be asked to complete a symptom diary card daily for the first seven days post colonoscopy FMT and then weekly thereafter for 26 weeks. The symptom diary card will help the patient monitor and keep track of adverse events. 6 months after the last dose of oral therapy, the patient will receive a final follow-up phone call.

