In addition the DSMB may convene additional meetings if necessary to ensure the ongoing monitoring and safety of the subjects treated with FMT. The internal DSMB will include the following individuals: [name] (Gastroenterology – BIDMC, Chair), [name] (Infectious Diseases – BIDMC), [name] (Gastroenterology – University of Pennsylvania)

All events will be reported directly to the DSMB and the Institutional Review Board (IRB) in accordance with Harvard University policy: Investigators will promptly report to the IRB all unanticipated problems involving risks to human subjects or others under Title 21 of the Code of Federal Regulations (21 CFR 312.32) part 56 (Institutional Review Boards), part 312 (Investigational New Drug Application), and part 812 (Investigational Device Exemptions). Harvard Medical School policy is consistent with guidance set forth by the Office for Human Research Protections (OHRP) (presented January 15, 2007)

<http://www.hhs.gov/ohrp/policy/AdvEvntGuid.htm> and the FDA (presented January 14, 2009) <http://www.fda.gov/downloads/RegulatoryInformation/Guidances/UCM126572.pdf> when determining what related events require review by the Institutional Review Board. Any serious AEs also will be evaluated by the DSMB for review and determination of whether the trial should continue.

All subjects will be followed for an additional six months following the end of their treatment. Subjects that did not experience a AEs or SAEs will receive a telephone call to monitor their current symptoms and quality of life. For subjects that did experience a AE or SAE that was found to be connected to the FMT treatment, we ask that they return to our medical center for an exam with their gastroenterologist. All treatment and outcome of AEs will be documented on the CRF and summarized in the CSR. All AEs will be followed to resolution or stabilization by the study physician.

9. Statistics

Power Calculations

Assuming 60% endoscopic recurrence in the control arm, and 20% in the FBT arm, the study would require 22 patients in each arm (Total N=44) to have 80% power. These assumptions are based on endoscopic recurrence data from the Reguero trial, which represents typical patient populations coming to ileo-colectomy at tertiary referral centers¹⁶. This cohort could be enrolled from 4 participating sites (N=11 per site) that perform >30 ileo-cecal resections per annum.

Statistical Analysis Plan

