For the primary end-point, chi-square test (or Fisher's exact test if any cell number <5) will be used to compare the proportion of patients in each arm who exhibit endoscopic recurrence (Rutgeerts score ≥ 12) at 6 months. A p value <0.05 will be considered significant.

For the secondary end-points, dichotomous variables will be summarized using frequency tables or proportions, and compared using chi-square or Fisher's exact test. Continuous variables will be expressed as mean values \pm standard error, and compared using unpaired, two-tailed Student's t-tests and one-way analysis of variance (ANOVA) for multiple group comparisons. Data that lack normality will be analyzed using non-parametric tests (Mann-Whitney). P-values < 0.05 will be considered significant, after correction for multiple tests. Data will be analyzed using JMP software (SAS, Cary, NC). For microbial diversity, we will apply a set of downstream statistical tests to the resulting microbial, viral, gene, pathway, and metabolite abundances. Transformed data from groups will be compared using Bray-Curtis similarity, multidimensional scaling, and analysis of similarity (ANOSIM) (Primer E, Plymouth, UK). ANOSIM will also be used to compare

intersubject and intrasubject TRFLP profile similarities. Analysis of variance (ANOVA) will be used to compare relative abundance of specific TRFLP pattern elements between each group of subjects. These tests will take into account covariates included in available or collected sample metadata (age, family history, treatment, environmental/demographic data, and diet) by leveraging our LEfSe univariate biomarker discovery method and its multivariate successor MaAsLin. Such statistical tests will provide a measure of expected reproducibility of predicted microbial biomarkers that is not attainable by unsupervised ordination methods (e.g. Principle Coordinates Analysis) as provided by other software such as QIIME.

10. Direct Access to Source Data/Documents

The investigator will permit trial-related monitoring, audits, IRB/IEC review, and regulatory inspection(s) by providing direct access to source data/documents.

11. Quality Control and Quality Assurance

Good Clinical Practice will be adhered to in screening, preparation and administration of donor stool. All research staff are trained in Responsible Conduct of Research of clinical trials.

12. Ethics

Special Ethical Considerations: None

Subject Confidentiality: as described above

Placebo Use: N/A

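### The between-arm percentage of patients with adverse events does not separate Crohn's recurrence from other events, so it can mix efficacy with harm, in a direction that depends on how the AE definition is applied to controls

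*Combined protocol and SAP*

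**What the plan says.** - **Definition.** Section 8 (Assessment of Safety) first describes an AE as "any untoward medical occurrence in a patient or clinical investigation patient administered a biologic product", with no causal link required. It then widens this to "any unfavorable and unintended sign, symptom, or disease temporally associated with the use of a medicinal product whether or not considered related". Hospitalization makes an event serious. Crohn's recurrence is neither named nor excluded.
- **Endpoints.** Section 7 lists two safety endpoints among the secondary endpoints: "Number and nature of adverse events at week 4, 12, 26 and 52", and the percentage "of patients with adverse events reported at week 4, 12, 26 and 52".
- **Test.** Section 9 (Statistical Analysis Plan) says that for secondary endpoints "dichotomous variables will be summarized using frequency tables or proportions, and compared using chi-square or Fisher's exact test". The percentage with AEs is dichotomous per patient, so it falls under this rule.
- **Who is assessed.** Section 4 (Recipient Procedures) screens both arms for AEs at weeks 4, 12 and 26 and again by telephone at week 52. Section 5 (Subject Withdrawal Criteria) keeps patients who need rescue in safety follow-up for 6 months, although they leave the primary analysis.
- **Recurrence during the trial.** Section 6 (Medications Permitted) states: "Rescue pathway for CD subjects with clinical recurrence during the study period to be determined by the clinician investigator". Hospitalization and surgery are among the options listed.
- **Expected rates.** Section 9 (Power Calculations): "Assuming 60% endoscopic recurrence in the control arm, and 20% in the FBT arm".

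**The concern.** Safety and tolerability are a stated objective and part of the hypothesis in Section 3. The percentage of patients with any AE is the safety summary that Section 9 would test between arms. A symptomatic flare fits the wide wording of the definition, and the trial expects more recurrence in controls than with FMT. The known FMT risks in the background section (altered bowel pattern, cramping) are also symptoms that a flare can produce.

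If flares enter the percentage, it reflects two things: harm caused by FMT, and recurrence that FMT is meant to prevent. These pull in opposite directions. Equal tolerability could then look like a safety advantage, and a real excess could shrink or change sign. Because the text is silent, each of the four planned sites would decide case by case, in an open-label trial where patients choose their arm.

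**Working it through.** **1. The plan's own figure.** The documents give no figure for the safety endpoints. The sample size for the primary endpoint (60% vs 20%, 80% power, 22 per arm) reproduces closely: the pooled-variance formula at two-sided 0.05 gives 23 per arm, and 22 per arm gives 79.4% power. So 60%, 20% and 22 per arm serve as inputs below.

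**2. Inputs.**
- From Section 9: recurrence r = 0.60 (control) and 0.20 (FMT), 22 per arm. These are endoscopic rates, not symptomatic flares.
- Assumed, because the documents give none: the share s of recurrences recorded as an AE; the rate a of AEs other than recurrence in each arm; and independence of the two.

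**3. Formula, flares recorded in both arms.** Reported rate = 1 - (1 - a)(1 - s × r).

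With a = 30% in controls and 50% with FMT (a true excess of 20 points):

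| s | Control | FMT | FMT minus control |
|---|---|---|---|
| 0% | 30.0% | 50.0% | +20.0 |
| 10% | 1 - 0.7 × 0.94 = 34.2% | 1 - 0.5 × 0.98 = 51.0% | +16.8 |
| 25% | 1 - 0.7 × 0.85 = 40.5% | 1 - 0.5 × 0.95 = 52.5% | +12.0 |
| 50% | 1 - 0.7 × 0.70 = 51.0% | 1 - 0.5 × 0.90 = 55.0% | +4.0 |
| 75% | 1 - 0.7 × 0.55 = 61.5% | 1 - 0.5 × 0.85 = 57.5% | -4.0 |

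The sign changes where 0.7(1 - 0.6s) = 0.5(1 - 0.2s), that is 0.20 = 0.32s, or s = 62.5%.

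With equal other-AE rates of 30%, FMT looks safer by 2.8 points at s = 10% (34.2% vs 31.4%), 7 at 25% (40.5% vs 33.5%) and 14 at 50% (51% vs 37%).

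**4. The literal reading.** If only patients given a product can have an AE by definition, control flares are not counted but FMT-arm flares are. In the 30% vs 50% example the control rate stays at 30%. The difference becomes 51.0 - 30 = 21 points at s = 10%, 52.5 - 30 = 22.5 at s = 25%, and 55 - 30 = 25 at s = 50%. The distortion now makes FMT look worse.

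**5. Effect on the test.** Exact power of Fisher's test, 22 per arm, two-sided 0.05, flares recorded in both arms:
- Other AEs 10% vs 40%: 55% with flares left out, then 37%, 18% and 5% at s = 10%, 25% and 50% (at s = 50% the reported rates are 37% vs 46%).
- Other AEs 30% vs 50%: only about 17% even with flares left out.

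Section 9 corrects secondary endpoints for multiple tests, so actual power would be lower in every case.

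**The case against.** A reader might infer that the definition makes Crohn's recurrence an AE and that FMT will therefore look safer than it is. The documents support neither step as a certainty.

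- **Silence and literal scope.** Recurrence is covered only by the breadth of the wording. Section 8 also ties AEs to patients given a product, and controls receive no therapy. Read that way, the bias reverses. This stands. Section 4 does screen controls for AEs, so the literal reading may not be intended, but the passages need to be reconciled.
- **Other separation in the plan.** The first safety endpoint covers the nature of events, so flares can be listed by type. Symptomatic recurrence has its own HBI endpoints and stopping criterion, and relatedness to FMT is judged for SAEs. This stands too: masking affects the crude percentage and the total count, not all safety reporting. A listing does not, however, repair a tested percentage, and sorting flares afterwards with the arm known is open to bias.
- **Invented inputs.** The share s and the other-AE rates are assumptions, 60% and 20% are endoscopic, and they cannot be carried to weeks 4 and 12. At s = 10% most of the excess survives. The size is therefore a range, not an estimate.
- **Direction.** The symptom diary and AE monitoring in Section 8 are timed from FMT, and the FMT arm has an observed first capsule dose and a follow-up call. Both could raise recorded AEs with FMT and offset the masking.
- **Net effect.** An all-cause percentage is a legitimate summary, and fewer flares is a real benefit. That argues for keeping it, not for showing it alone.

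**Conclusion.** The concern holds in a conditional form. The plan tests an undivided percentage under an all-cause definition that has no rule for Crohn's recurrence and is unclear about controls. Given that FMT works, recording flares in both arms understates FMT-caused harm at every s above zero. In the 30% vs 50% example the loss runs from about 3 points at s = 10% to 24 points at s = 75%. Under the literal definition the distortion goes the other way, by 1 to 5 points for s from 10% to 50%.

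These figures rest on the plan's endoscopic rates, assumed AE rates, independence and an unknown s. The net direction also depends on unequal contact between arms. It would be wrong to conclude that the safety comparison as a whole is invalid, or that separating flares would make it well powered: a 20-point excess from 30% has about 17% power at 22 per arm in any case. No sample-size figure changes. This is a cheap improvement to a stated objective.

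**What to change.** 1. In Section 8, word the AE definition so that it expressly covers both arms. Leave its all-cause scope unchanged for DSMB and IRB reporting.
2. Add a Crohn's-recurrence flag to the AE form, set from one pre-listed set of terms applied identically in both arms. Do not let the rescue decision set the flag: rescue is at the investigator's discretion and the trial is open-label.
3. In Section 9, report and compare AEs and SAEs by arm both including and excluding flagged events, side by side and with equal standing.

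The cost is one sentence, one form field and a few table rows. The downside is that some FMT-caused bowel symptoms may be flagged as Crohn's and leave the second version, so neither version should be treated as the sole main comparison.
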